To revise the existing inclusion criterion for hemoglobin A1c (HbA1c) to align with the observed distribution at study sites so that the study can consider a wider patient population as potential study participants without impacting study participants' safety and study data integrity. Additional clarifications were made as outlined in the table below.

Section # and Name	Description of Change	Brief Rationale		
Section 1.1. Synopsis and Section 3. Objectives and Endpoints	In the first secondary endpoint, added predose BG in parenthesis, deleted plasma from parenthesis, and replaced plasma with blood.	To provide additional information and clarification		
Section 1.3. Schedule of Activities (SoA)	Included SC injection of insulin as an option for MDI users	Added for consistency with Section 4.1.4.		
Section 3. Objectives and Endpoints	In the exploratory endpoint, added predose BG in parenthesis and replaced plasma with blood	To provide additional information and clarification		
Section 4.1.4. Day 1: Predose	Included SC injection of insulin as an option for MDI users	Added for flexibility in treatment options for MDI users		
Section 4.1.5. Day 1: Dosing	NG will be administered within 5 minutes of baseline BG measurement changed as predose BG measurement	Correction to state that NG administration to be done within 5 minutes of predose BG rather than from baseline BG		

Section # and Name	Description of Change	Brief Rationale
Section 5.1. Inclusion Criteria	In inclusion criterion 4, increased the HbA1c level from ≤ 9.0 to $\leq 9.5\%$	To revise the existing inclusion criterion for HbA1c to align with the observed distribution at study sites so that the study can consider a wider patient population as potential study participants without impacting study participants' safety and study data integrity.

Table of Contents

1.	Protocol Summary	8
1.1.	Synopsis	8
1.2.	Schema	9
1.3.	Schedule of Activities (SoA)	10
2.	Introduction	
2.1.	Study Rationale.	
2.2.	Background	16
2.3.	Benefit/Risk Assessment	
2.3.1.	Risk Assessment	17
2.3.2.	Benefit Assessment	19
2.3.3.	Overall Benefit: Risk Conclusion	19
3.	Objectives and Endpoints	21
4.	Study Design	
4.1.	Overall Design	
4.1.1.	Screening	
4.1.2.	Predosing-Visit Telephone Reminder	
4.1.3.	Day 1: Call/Text on Morning of Dosing	
4.1.4.	Day 1: Predose	
4.1.5.	Day 1: Dosing	
4.1.6.	Day 1: Postdose	
4.1.7.	Follow-up	
4.1.8.	Rescheduling Visits	
4.2.	Scientific Rationale for Study Design	
4.3.	Justification for Dose	

1.1. Synopsis

Protocol Title: An Open-Label, Multi-Center, Single-Dose Study to Assess the Safety, Tolerability, Pharmacodynamics, and Pharmacokinetics of Nasal Glucagon in Pediatric Patients with Type 1 Diabetes Aged 1 to <4 years

Short Title: A Single-Dose Study to Assess Nasal Glucagon in Pediatric Patients with Type 1 Diabetes aged 1 to <4 years

Rationale: The primary aim of Study I8R-MC-IGBO (IGBO) is to assess the safety and tolerability of a 3 mg dose of NG (commercial drug product) in pediatric participants aged 1 to <4 years with T1D in an inpatient clinical research facility.

Objectives	Endpoints			
Primary				
To assess the safety and tolerability of a single dose of NG 3 mg in children aged 1 to <4 years with T1D	Incidence of treatment-emergent adverse events.			
Secondary				
To assess the PD of a single dose of NG 3 mg in children aged 1 to <4 years with T1D	Change from baseline (predose BG) of maximum blood glucose. Other blood glucose parameters: BGmax AUC TBGmax			
To assess the PK of a single dose of NG 3 mg in children aged 1 to <4 years with T1D	Model-estimated population PK parameters			

Objectives and Endpoints

Overall Design: Study IGBO is a Phase 1, open-label, multi-center study with a primary objective of assessing safety and tolerability of a single 3 mg dose of NG in pediatric participants aged 1 to <4 years with T1D.

Participants will attend study visits, including screening, in the company of 1 or more parents or legal guardians, and in accordance with local healthcare facility practice.

The study comprises a single cohort, with each participant receiving a single dose of 3 mg NG.

Disclosure Statement: This is a single-arm, open-label pediatric study.

Number of Participants: At least 9 participants with an approximate maximum of 20 may be enrolled so that 6 evaluable participants complete the study.

Intervention Groups and Duration:

Each participant is expected to participate in the study for up to approximately 7 weeks, from screening through follow-up.

Data Monitoring Committee: No

1.2. Schema

* Predosing-visit telephone call is not required if screening takes place on Day -1.

1.3. Schedule of Activities (SoA)

Procedure	Screening Visit	Predosing-visit preparation reminder (telephone)	Dosing Visit	Follow-up (telephone)	Second Follow-up (telephone)	Comments
	Day -35 to Day -1	Day -1	Day 1	Day 2	Day 9±3	
Informed consent	х					Provided by parent/legal guardian. Should be obtained before any study-related procedures are performed. May be obtained during a separate informed consent visit to the site.
Demographics	Х					Full date of birth (day, month, year), sex, and ethnicity will be collected, if consistent with local regulations.
Medical history	Х					
Education on specifics of dosing visit	Х	Х				Discussion between site staff and parent/legal guardian on the target blood glucose range and information for dosing visit. See Section 5.1.
Eligibility	Х					See Section 5.
Height	Х					
Weight	X		X			On Day 1, body weight will be measured predose.

Procedure	Screening Visit	Predosing-visit preparation reminder (telephone)	Dosing Visit	Follow-up (telephone)	Second Follow-up (telephone)	Comments
	Day -35 to Day -1	Day -1	Day 1	Day 2	Day 9±3	
Vital signs (body temperature, blood pressure, pulse rate)	х		Х			See Section 8.2.2. On Day 1, vital signs should be measured predose and 45 min postdose. Time points may be added on Day 1 if warranted, at the discretion of the investigator.
Clinical laboratory tests	Х					See Appendix 2 (Section 10.2) for details. Participants do not need to fast for laboratory samples. Laboratory tests will be processed at a local laboratory.
Age-appropriate physical examination	Х					
Adverse event assessment	Х		Х	Х	Х	AE assessment at telephone follow-up requires conversation with parent/legal guardian about any AEs experienced by the participant.
Concomitant medication assessment	Х		Х	Х	Х	On Day 1, concomitant medication assessment should be conducted predose.
Pre-admission contact from site to parent/legal guardian			Х			Contact parent/legal guardian to check BG levels are suitable for study procedures. Before participant and parent/legal guardian leave home, within approximately 2 hours before dosing.

Procedure	Screening Visit	Predosing-visit preparation reminder (telephone)	Dosing Visit	Follow-up (telephone)	Second Follow-up (telephone)	Comments
	Day -35 to Day -1	Day -1	Day 1	Day 2	Day 9±3	
Admission to site			х			It is recommended that participants have a natural overnight fast if possible, assuming morning dosing. At a minimum, participants should have no food or beverage intake other than water within 3 hours before dosing.
Verification of hypoglycemia history since screening			Predose			See Section 5.2.1.
Allocation of participant enrollment number			х			Once eligibility is confirmed and participant is ready for dosing.
Baseline glucose measurement			Х			See Section 4.1.4.

Procedure	Screening Visit	Predosing-visit preparation reminder (telephone)	Dosing Visit	Follow-up (telephone)	Second Follow-up (telephone)	Comments
	Day -35 to Day -1	Day -1	Day 1	Day 2	Day 9±3	
If necessary to achieve target glucose level, adjust basal rate or administer a small bolus via insulin pump; or for MDI, infuse a small correction bolus of insulin diluted in normal saline through IV or by SC injection			Predose			At PI's discretion. See Section 4.1.4.
Nasal inspection	Х		Predose, 90 min			Visual nasal inspections. On Day 1, the predose inspection, administration of NG, and postdose inspection (90 min) should all be done by the same person.
Return insulin pump basal rate to pre- study settings			Postdose			For pump users only. If basal rate was adjusted to achieve target blood glucose on the study day, the basal rate must be returned to participant's normal rate prior to discharge.

Procedure	Screening Visit	Predosing-visit preparation reminder (telephone)	Dosing Visit	Follow-up (telephone)	Second Follow-up (telephone)	Comments
	Day -35 to Day -1	Day -1	Day 1	Day 2	Day 9±3	
NG administration			х			Nasal glucagon will be administered only if a participant's baseline glucose level is within target range. See Section 4.1.4.
Sample collection for measurement of plasma glucagon (pharmacokinetics)			10, 30, 60 min			Time points are relative to NG administration.
Bedside glucose safety measurements			Х			Measured using a point-of-care blood glucose testing device: either CGM, if applicable, via IV cannulation, or using an approved BG meter. See Section 8.2.4.1. Blood glucose readings will be taken every 5 to 10 min for the first 30 min after dosing, and then every 20 min up to 90 min. Additional measurements may be taken at investigator's discretion. When a planned bedside safety sample coincides with a PD sample, the PD sample may be used for bedside safety assessment.
Sample collection for measurement of plasma glucose (pharmacodynamics)			P, 10, 30, 60, 90 min			Measured with study-approved rapid glucose analyzer (Section 8.6). Timings are relative to NG administration.

Procedure	Screening Visit	Predosing-visit preparation reminder (telephone)	Dosing Visit	Follow-up (telephone)	Second Follow-up (telephone)	Comments
	Day -35 to Day -1	Day -1	Day 1	Day 2	Day 9±3	
Meal			Х			Following completion of all study procedures, the participant will be provided a meal including carbohydrates, and the investigator will ensure the participant's plasma glucose is stable prior to discharge.
Discharge from site			Х			Participants may be discharged after 4 hours postdose safety monitoring is complete. If required, a participant may remain in clinic for further observation, at the discretion of the investigator.

Abbreviations: AE = adverse event; BG = blood glucose; CGM = continuous glucose monitoring; IV = intravenous; MDI = multiple daily injection; NG = nasal glucagon; P = predose; PD = pharmacodynamics; PI = principal investigator; SC = subcutaneous.

2. Introduction

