2.3.1.1. Risks and Safety Considerations in Study IGBO

Baseline glucose target level

Prior to dosing, each participant's baseline glucose level should be within a target range of 70 to 140 mg/dL for NG to be administered. This range is based on premeal target glucose values recommended by the ISPAD (DiMeglio et al. 2018) of 70 to 130 mg/dL, with a +10 mg/dL allowance for the upper limit.

Refer to the Study Operations Manual for detailed instructions.

This study avoids the induction of hypoglycemia (defined as BG <70 mg/dL; Abraham et al. 2018), to ensure there is no more than a minimal increase in medical risk for the pediatric population.

The investigator may consider rescue medication to pre-empt or treat clinically significant or severe hypoglycemia if indicated by the baseline BG level.

If a participant's baseline BG level is

- <70 mg/dL, the investigator will determine whether to proceed with dosing or to use rescue treatment (Section 8.3.6).
- <54 mg/dL (clinically significant hypoglycemia [Level 2]), site will halt study drug procedure and use rescue therapy to raise BG level.

If rescue therapy is administered, the participant should remain at the site until stable based on investigator observation and clinical judgment. The visit may be rescheduled for a subsequent day at the investigator's discretion, and according to the Manual of Operations.

If the participant does not return to the site for a subsequent visit in which required study procedures are completed, the participant must be discontinued from the study.

Blood sampling

The number and volume of blood samples for each participant have been minimized to reduce the potential risks and lower the burden of study procedures for pediatric participants.

Glucose safety monitoring

Though hypoglycemia is not induced in this study, there is the potential for a participant to experience hypoglycemia. Participants' BG level will be monitored at the bedside during and after NG administration, and the investigator may consider use of glucose or glucagon to

pre-empt or treat severe hypoglycemia. See Section 8.2.4.1 for details on this bedside glucose safety monitoring, and Section 8.3.6 for detail of the rescue procedure.

Needle punctures

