4.1.2. Predosing-Visit Telephone Reminder

On Day -1, site staff will telephone the participant's parent/legal guardian to give a reminder about the procedure for dosing day, including

- the recommendation that participants have a natural overnight fast if possible, assuming morning dosing. At a minimum, participants should have no food or beverage intake other than water within 3 hours before dosing,
- the target BG level, and

• that site staff will be in contact on the morning of dosing to determine whether the participant's BG level is likely to be in the required range for dosing.

Note that this postscreening call may be omitted if the screening visit was on Day -1.

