4.1.4. Day 1: Predose

For the dosing visit (Day 1), it is recommended that participants have a natural overnight fast if possible, assuming morning dosing. At a minimum, participants should have no food or beverage intake other than water within 3 hours before dosing.

At the study site, BG will be measured to determine if the participant's baseline BG level is within the target range of 70 to 140 mg/dL (Section 2.3.1.1), and confirm ability to proceed with dosing and other study procedures.

If BG is

- below the target range, rescue treatment may be considered (Section 8.3.6).
- above the target range, the investigator may choose to
 - in the case of pump users, increase the basal insulin rate of the participant's insulin pump, or initiate a small bolus dose, to achieve target BG
 - in the case of MDI users: administer a small correction bolus via SC injection of insulin or IV infusion of insulin diluted in normal saline to achieve target BG
 - wait and allow BG to decrease to target level if BG is already decreasing, or
 - \circ reschedule the visit (Section 4.1.8).

If a bolus dose of insulin is administered via the pump, or insulin is administered to patients on MDI, the dose level will be based on PI discretion.

The basal rate or insulin infusion may be adjusted at the discretion of investigator during study procedures as necessary to protect participant safety.

For pump users only, if the investigator adjusts the pump basal rate setting, it may be returned to pre-study settings after 90 minutes postdose and all PK and PD samples have been collected, at the discretion of investigator. The basal rate setting must be returned to participant's usual setting prior to discharge. Additionally, site staff must confirm the basal settings with the parent/legal guardian before the participant is discharged.

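### For a baseline glucose of 54 to <70 mg/dL, the protocol and SAP both rule out and permit dosing with nasal glucagon

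*Protocol*

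**What the plan says.** **Text that makes an in-range baseline a condition of dosing**

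- Protocol Section 1.3 (SoA), NG administration row: "Nasal glucagon will be administered only if a participant's baseline glucose level is within target range". The row refers to Section 4.1.4.
- Protocol Section 2.3.1.1, opening sentence on the glucose target: "each participant's baseline glucose level should be within a target range of 70 to 140 mg/dL for NG to be administered".
- Protocol Section 4.1.4: "BG will be measured to determine if the participant's baseline BG level is within the target range of 70 to 140 mg/dL". For a value below range, this section says only that rescue may be considered. It does not list dosing as an option.

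**Text that leaves dosing to the investigator**

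- Protocol Section 2.3.1.1, bullet for a baseline below 70 mg/dL: "the investigator will determine whether to proceed with dosing or to use rescue treatment". Protocol Section 8.3.6.1 and SAP Section 10.6.2 carry the same provision.
- In all three places the mandatory stop applies only below 54 mg/dL, where the "site will halt study drug procedure and use rescue therapy to raise BG level".

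**Text that bears on how to read the two**

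- Section 2.3.1.1 says the study "avoids the induction of hypoglycemia (defined as BG <70 mg/dL").
- Section 8 describes the SoA as a summary of procedures and timing. It also makes adherence to the SoA obligatory and allows no waivers.
- Section 2.3.1.1 adds: "Refer to the Study Operations Manual for detailed instructions".

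**The concern.** The SoA row is an exclusive condition with no exception, while three other places assume that a child below 70 mg/dL may be dosed if the investigator so decides. Between 54 and 70 mg/dL these cannot both be followed as written.

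Two things are at stake. The first is who receives study drug: the participants are 1 to <4 years old, Section 2.3.2 anticipates no therapeutic benefit for them, and every child in the disputed band already meets the protocol's definition of hypoglycemia. The second is how such dosing is classified. Under the SoA wording it is a deviation; under the discretionary wording it is permitted conduct. SAP Section 9 weighs deviations for severity and impact when assigning patients to analysis populations, so the classification can reach the PD and efficacy summaries.

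**Working it through.** The plan states no figure to reproduce for this point. The check is to apply each rule at values on either side of every threshold.

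**Inputs.** Range limits of 70 and 140 mg/dL (Sections 2.3.1.1 and 4.1.4); discretion below 70 mg/dL and halt below 54 mg/dL (Sections 2.3.1.1 and 8.3.6.1, SAP Section 10.6.2); Section 4.1.4 for values above range. The <54 mg/dL bullet is read as overriding the <70 mg/dL bullet, so discretion covers 54 to <70 mg/dL.

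| Baseline (mg/dL) | SoA condition | Detailed text | Result |
|---|---|---|---|
| 50, 53 | no dose | halt and rescue | agree |
| 54, 60, 69 | no dose | investigator decides | conflict |
| 70, 140 | dose allowed | dose allowed | agree |
| 141 | no dose | insulin, wait or reschedule | agree |

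The conflict is confined to 54 to <70 mg/dL. In whole-number readings that is 69 - 54 + 1 = 16 values, all below the 70 mg/dL definition of hypoglycemia and none below the 54 mg/dL halt. This is the width of the band, not a count of children.

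**Can the texts be read together?**

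1. Section 2.3.1.1 falls on both sides: its opening sentence makes the range a condition for administration, and its bullet gives discretion below it. The conflict is therefore not only between a table and the body text.
2. The discretionary text could mean dosing later, once glucose has recovered. It does not say so, and it offers dosing as the alternative to rescue.
3. The SoA row leads to Section 4.1.4, which leads to Sections 2.3.1.1 and 8.3.6. The discretion is thus two references away from the row, and Section 4.1.4 itself does not mention dosing a child who is below range.

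**Which reading is the gate?** Section 4.1.4 describes an on-site check that may be followed by waiting or, for high values, insulin. Section 4.1.5 times dosing from a predose measurement. The endpoint table in Section 3 equates baseline with the predose value. No text says whether the on-site check or the predose value decides eligibility for dosing, and the two could fall on different sides of 70 mg/dL.

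**Effect on planned tests.** SAP Sections 10.3.2, 10.4.2 and 10.6.8 each state that no inferential analysis is planned, so the number of planned tests affected is 0.

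**The case against.** The strongest reply is that the SoA is a summary. It sits under the Protocol Summary, Section 8 describes it that way, and its own cross-reference leads to detailed text that gives the discretion explicitly, in nearly the same words in three places. A site could reasonably take the detailed provision as the working rule. This has weight: it makes the discretionary reading plausible. It does not settle the matter, because Section 8 also makes the SoA binding and bars waivers, and nothing presents the discretion as an exception. The Study Operations Manual is not available here. It may contain a working rule, but that would not reconcile the protocol and SAP.

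Several stronger readings are tempting, and the documents do not support them.

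- *That the restriction recurs throughout the protocol.* Section 4.1.2 refers to "whether the participant's BG level is likely to be in the required range for dosing", but that is part of a reminder to parents. Section 4.1.5.1 governs a second attempt after a suspected failed administration, not baseline. Section 4.1.8 only permits rescheduling. None is a second baseline gate.
- *That the contradiction causes differences between sites.* Any rule resting on investigator discretion allows those. The contradiction adds uncertainty about what is permitted and what counts as a deviation.
- *That such dosing would be untraceable.* SAP Section 10.6.2 does keep bedside readings, including those at baseline, out of the database. But the predose analyzer glucose is collected and listed (SoA; SAP Section 10.4.2), SAP Section 10.6.2 provides a hypoglycemia event form, and source data verification applies (Protocol Section 10.1.6). The gap is partial.
- *That the bedside-monitoring thresholds announced but not listed in Section 8.3.6.1 support this point.* They are a separate matter.

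**Conclusion.** The contradiction is real, lies in current text, and covers exactly 54 to <70 mg/dL. It should be resolved because it concerns a dosing gate in very young children, not because of statistical harm. No planned test is biased, the analyses are descriptive, and the Safety population keeps every dosed child.

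The documents give no basis for estimating how many children would present in the band, and none is claimed; the screening education, reminder call and morning glucose check are meant to bring children in on target. For scale only: with the planned 6 evaluable participants, one child is 1/6 = 17% of a PD or efficacy summary, so a population decision about a single such child would be visible if it arose.

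The conclusion assumes that the <54 mg/dL halt overrides the <70 mg/dL discretion and that the discretionary text means dosing without prior recovery, as its wording suggests. It takes no view on which clinical rule is right.

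**What to change.** - Reconcile the SoA NG administration row, Protocol Sections 2.3.1.1, 4.1.4 and 8.3.6.1, and SAP Section 10.6.2, so that a single rule covers a baseline of 54 to <70 mg/dL. The choice of rule belongs to the sponsor and its clinicians.
- State which on-site reading gates dosing, and define a protocol deviation against that same reading, so that SAP Section 9 can be applied consistently.
- Check the second-attempt wording in Section 4.1.5.1 against the reconciled rule.
- Optional: if the gating reading is not the predose PG sample already listed, record it in the eCRF and adjust the SAP Section 10.6.2 sentence on databasing for that one value.

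The cost is wording in a protocol amendment and one or two SAP sentences, plus one eCRF field if the option is taken. The reading is already taken on Day 1, so no extra participants, samples or procedures are needed.

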2.1. Study Rationale

The primary aim of Study I8R-MC-IGBO (IGBO) is to assess the safety and tolerability of a 3 mg dose of NG (commercial drug product) in pediatric participants aged 1 to <4 years with T1D in an inpatient clinical research facility.

